9.14 Schedule of data collection

We will collect a variety of information from the mother-infant pairs enrolled in the prospective and extension cohort throughout the study, as shown in Table 7. Table 7.1 shows the data collection time for the prospective cohort 6-month extension. The additional phone check-ins (are around 7.5 and 10.5 months) are only applicable for Tanzania and/or Malawi.

Table 7: Data collection schedule for prospective cohort

Weeks and months of infant's life	Baseline	Weekly for first 6 weeks				Monthly				
		0	1	2	4	6	2	3	4	6
Demographics and pregnancy history	✓	✓								
Gestational age	✓									
Infant anthropometrics	✓	✓	✓	✓	✓	✓	✓	✓	✓	
Maternal anthropometrics	✓				✓					✓

Infant feeding/maternal lactation questionnaire	✓	✓	✓	✓	✓	✓	✓	✓	✓
Infant health questionnaire	✓	✓	✓	✓	✓	✓	✓	✓	✓
Maternal health questionnaire	✓	✓	✓	✓	✓	✓	✓	✓	✓
Home Water/Sanitation Assessment						As required			
Sick visit or inpatient data						As required			
Mortality						As required			

Table 7.1: Data collection schedule for prospective cohort extension

Months of infant's life	Monthly			
	7.5	9	10.5	12
Demographics and home environment		✓		✓
Well-being		✓		✓
Infant anthropometrics		✓		✓
Maternal anthropometrics				✓
Infant feeding/maternal lactation	✓	✓	✓	✓
Infant health	✓	✓	✓	✓
Maternal health	✓	✓	✓	✓
Home Water/Sanitation Assessment		✓		✓
Mortality	✓	✓	✓	✓

9.15 Location of follow up visits

Mothers will return to the facility with their infants for each follow-up visit. Based on site requirement, clinic-based visits or home visits will be conducted in the early neonatal period. If the mother misses a facility visit, then study staff will make a home visit.

6-month extension: same procedures apply though home visits will be more prevalent.

9.16 Data collection at sick visits

If an enrolled infant falls ill, the mother may bring the child to the facility for a sick visit, unrelated to the study. The sick visit will present an opportunity to collect additional data on the illness as well as lactation and growth of the infant.

To collect this data, we would like to identify the mother-infant pair as enrolled in the study. Each site will establish a simple process to achieve this. For example, in Malawi, study participants will have a study appointment card attached to their health passport, listing the participant study number, visit schedule, and contact details of lead study staff. Also, study patients will be advised to come to the study clinic when they are sick, or to contact the study team if they seek care elsewhere or are hospitalized. In India, enrolled patients will be advised to return to the facility in case of illness, and also given a trial card with instructions to other physicians to inform the study investigator if they seek care elsewhere.

For all infants presenting for a sick visit: we will ask the mother questions about the infant's illness and any changes in feeding due to that illness, and we will weigh the infant at the time of the visit / admission to health facility. In the event that an infant is admitted to the health facility, we will ask the mother additional questions about the infant's stay in the hospital, and study staff will review chart documentation to gather additional data about the infant's diagnosis. We will also weigh the infant at the time of discharge from the health facility.

Prior to any data collection occurring at sick visits or health facility admission, the study team will confirm it is appropriate to proceed with data collection with the baby's health care provider. The study team will also confirm the mother is comfortable with the sick study visit prior to proceeding. The study team will develop an internal SOP regarding culturally appropriate criteria for approaching families in the health facility.

6-month extension sick visit: These sick visits are not applicable and will not be implemented during the additional 6 months of follow up. Additional information on illnesses will be collected in the revised prospective extension cohort follow up tool rather than a separate sick visit tool.

9.17 Data collection at home visits

In the event that a mother cannot come to the facility for a follow up visit, a home visit will be made by study staff. As above, visits in the early neonatal period will be conducted at the facility or home per site requirements. The mother, father, and other family members will be informed in advance of these visits so they are not surprised. At the home visit, study staff will complete the same measures as for the facility visit, unless they are not possible due to lack of equipment.

The home environment, a critical factor in the safety of infant feeding, will be important to understand when designing a safe IYCF intervention. During the home visit, study staff may separately collect supplemental information on WASH in the home environment for a sample of mothers at selected follow-up timepoints. This potential data collection would be restricted to documenting observable measures and equipment. We would not collect biological samples, unused supplies, or swabs of containers.

In addition, the mother will be asked to use the illness diary (morbidity diary) that will be provided to the mother during the initial 6-week visit. The purpose of the diary is to record details on specific illnesses experienced by the baby (diarrhea, vomiting, fever and respiratory infections) in between study visits. At each follow-up visits, the mother will bring the completed illness diaries to the study team and will be given a fresh set of blank illness diaries for the next visit.

6-month extension: Same procedures will be followed with some modification to the questions.

9.18 Study measures

9.18.1 Demographics, pregnancy history and home environment

At baseline and at 9 and 12 months, we will ask the mother to respond to a questionnaire with basic socio-demographic information such as age, education level, marital status, and home environment. These variables and response categories will likely differ somewhat by site.

The questionnaire will also cover a detailed pregnancy history, access to antenatal care (ANC), supplementation during pregnancy, food and water insecurity, household water, sanitation and hygiene (WASH) conditions, and related topics. Not all questions will be asked in the last 6 months versus the first.

Some demographic and household WASH questions will be asked at the Week 1 follow-up visit to minimize the number of questions asked to the mother at baseline (shortly after delivery)

9.18.2 Gestational age (baseline visit only)

Measuring gestational age is notoriously difficult. Prematurity and intrauterine growth restriction are the primary causes of LBW. We anticipate that there will be physiologic differences between these groups, but also acknowledge the challenges in accurate identification of gestational age in this study population due to limitations in prenatal care and use of early ultrasound. The availability and quality of gestational age data will be highly variable between study sites. Only one site (India-Karnataka site) will have access to early pregnancy ultrasonography, because of the presence of an existing trial for antenatal corticosteroid. In the remaining sites, the majority will likely not have access to ultrasound dating and will rely on last menstrual period (LMP) or Symphysis fundal height, as per standard of clinical care. We will capture what gestational age information is available from the woman's antenatal card, ultrasound history, etc. In cases where ultrasound data is available (either through clinic records or maternal self-report), we will consider this to be the first preference for gestational age dating. We will also ask the mother the date of her last menstrual period (LMP), and use this information as second preference for gestational age dating if ultrasound results are not available.

Given the poor quality and availability of antenatal dating in some sites, the LIFE study will also need to rely on neonatal assessment for gestational age dating. In a recent systematic review, 18 different neonatal assessments for gestational age dating were identified in the literature (Lee 2017). The most commonly used, simpler and feasible assessments, such as the Ballard or Capurro, were inaccurate, dating pregnancies to +/- 4 weeks of ultrasound dating. The Dubowitz exam was found to be the most accurate, dating 95% of pregnancies within +/- 2.6 weeks of an

ultrasound based date. However, the Dubowitz exam includes 21 signs including neurologic and external physical signs, and the feasibility of training, standardization and use in LMIC requires further programmatic research.

We propose to use the Dubowitz exam for gestational age dating in the LIFE study, and in the formative phase will assess the feasibility of training and standardization of this assessment across the four study sites. The Every Newborn Action Plan Metrics Group prioritized the assessment of the feasibility of implementation of the Dubowitz exam as a research priority for gestational age dating in LMIC.

For multiples enrolled in the study, we will determine gestational age for one baby and infer the same gestational age for the other twin or triplets.

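### Gestational age dating ranks any ultrasound first, whatever its timing and even by maternal recall, and leaves the Dubowitz exam without a rank or a disagreement rule

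*Combined protocol and SAP*

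**What the plan says.** Section 9.18.2 of the combined protocol and SAP makes four statements that bear on dating.

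- **Rank 1, ultrasound.** "In cases where ultrasound data is available (either through clinic records or maternal self-report), we will consider this to be the first preference". There is no upper limit on gestation at the scan, and a report from the mother counts the same as a record.
- **Rank 2, LMP.** The plan will "use this information as second preference for gestational age dating if ultrasound results are not available". No reliability check is attached.
- **Availability.** "Only one site (India-Karnataka site) will have access to early pregnancy ultrasonography". Elsewhere, "the majority will likely not have access to ultrasound dating and will rely on last menstrual period (LMP) or Symphysis fundal height". Fundal height gets no rank.
- **Neonatal assessment.** "Given the poor quality and availability of antenatal dating in some sites, the LIFE study will also need to rely on neonatal assessment". Then: "We propose to use the Dubowitz exam for gestational age dating in the LIFE study", with feasibility still to be assessed. For multiples, one infant is dated and the result is applied to the siblings.

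Section 9.20 uses the result twice. The 37-week cut decides between the INTERGROWTH-21st preterm standards and the WHO standards. The extension's longitudinal models test whether growth differs by gestational age and by size for gestational age at birth.

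**The concern.** A scan late in pregnancy infers gestation from fetal size, so a growth-restricted fetus reads as younger than it is. This is a general property of size-based dating and is not stated in the plan. All infants in this cohort weigh 1500 to under 2500 g at birth (section 9.1), and section 9.18.2 names prematurity and growth restriction as the main causes. Errors from late scans would therefore tend to run one way: a term, small-for-age infant is recorded as preterm and appropriate for age. Those are the two groups the plan expects to differ.

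The second gap is the missing rule for Dubowitz. Take an infant with both an LMP and a Dubowitz score that fall on opposite sides of 37 weeks. Ranking LMP second suggests that LMP decides. Adopting Dubowitz for dating in the study suggests that Dubowitz may decide. Two analysts could classify the same infant differently and both follow the plan.

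**Working it through.** **1. Which infants each gap reaches.** Outside Karnataka most infants are expected to have no ultrasound, so the scan rule reaches a minority there. The open LMP/Dubowitz order reaches the rest. At Karnataka, access to early scans does not exclude a late or recalled one, and the rule has no timing limit there either.

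**2. Errors the documents do give.** Dubowitz: "The Dubowitz exam was found to be the most accurate, dating 95% of pregnancies within +/- 2.6 weeks of an" ultrasound-based date. If the error is normal and unbiased, SD = 2.6 / 1.96 = 1.33 weeks. Ballard and Capurro: "such as the Ballard or Capurro, were inaccurate, dating pregnancies to +/- 4 weeks of ultrasound dating". If that is a 95% range, SD = 4 / 1.96 = 2.04 weeks. No error is given for LMP, late scans or recalled scans.

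**3. Illustration of a 1-week under-dating.** Assume gestational age (GA) is normal. Every infant truly between 37 and 38 weeks then crosses the cut, a share of Φ((38 − mean)/SD) − Φ((37 − mean)/SD).

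- Mean 35.5, SD 2.5: Φ(1.0) − Φ(0.6) = 0.841 − 0.726 = 0.116
- Mean 35.5, SD 2.0: Φ(1.25) − Φ(0.75) = 0.894 − 0.773 = 0.121
- Mean 37, SD 2.5: Φ(0.4) − Φ(0) = 0.655 − 0.500 = 0.155
- Mean 37, SD 2.0: Φ(0.5) − Φ(0) = 0.691 − 0.500 = 0.191

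So 12-19% of infants dated by such a scan move from term to preterm. The mean, the SD and the shift are all assumed.

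**4. Comparison with Dubowitz-size error.** I simulated observed GA = true GA + error (2 million draws) and classified at under 37 weeks. The assumed late scan has a bias of −1 week and the same SD of 1.33.

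| True GA mean, SD | Truly preterm | Dubowitz: wrong side / labelled preterm | Late scan: wrong side / labelled preterm |
|---|---|---|---|
| 35.5, 2.0 | 77.4% | 14.9% / 73.4% | 13.8% / 85.1% |
| 36.5, 2.0 | 59.9% | 18.2% / 58.2% | 20.2% / 73.4% |
| 36.5, 2.5 | 57.9% | 15.3% / 57.0% | 17.7% / 70.2% |
| 37.5, 2.0 | 40.2% | 18.2% / 41.8% | 23.9% / 58.3% |

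The share on the wrong side is similar in the first row and higher for the late scan in the others. The clearer difference is direction. The preterm share shifts by −4 to +2 points with Dubowitz-size error and by +8 to +18 points with the late scan. Among truly term infants, 35-48% are labelled preterm with a 1-week bias and 57-71% with a 2-week bias, against 17-24% with Dubowitz-size error.

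**5. LMP against Dubowitz.** With unbiased error of SD 1.0, 1.5, 2.04, 2.5 or 3.0 weeks, the share on the wrong side is 12-14%, 17-20%, 21-25%, 25-28% or 27-31%. LMP does worse than Dubowitz only if its error SD exceeds about 1.33 weeks, and the documents do not say whether it does.

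**6. Planned precision.** Section 9.12 gives ±2.7% for a 5% proportion in 250 infants: 1.96 × √(0.05 × 0.95 / 250) = 0.027. It reproduces and does not depend on dating.

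**The case against.** The strongest defence is that the plan acknowledges the problem. It calls antenatal dating poor in some sites, adds neonatal assessment for that reason, and trains staff in it (section 6.3). Eligibility rests on birthweight. The main results are rates, such as unsuccessful breastfeeding or tube feeding (section 9.12), which do not need gestational age. Sites are to be analysed separately (section 2.1), so uneven dating quality is not pooled by design. Every dating method misclassifies some infants, Dubowitz included.

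Much of this stands, and it rules out three stronger readings that a reader might infer.

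- *LMP outranks Dubowitz.* Ranking LMP second hints at this, but the plan proposes Dubowitz for the study without limiting it to infants who lack a scan or LMP. Its place is undefined.
- *Preterm and size-for-age status will be misclassified in the three sites without early scans.* Most infants there are expected to have no ultrasound, and without an error figure for LMP or for late or recalled scans the documents cannot show that this order adds error.
- *The plan itself says that only early ultrasound is reliable.* It does not. It cites limited early ultrasound as a difficulty and quotes Dubowitz accuracy against ultrasound dating with no timing qualifier.

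The illustration in step 3 also shifts every infant dated by a late scan, whereas the argument applies to growth-restricted fetuses, so it leans high.

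The defence does not supply a timing limit or record requirement for scans, or a rule for disagreement. Separate analysis by site does not correct a biased classification within a site.

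**Conclusion.** The concern holds as a defect in the dating rule. First preference goes to scans of any timing and to recalled scans, and the place of Dubowitz is open, so preterm/term and size-for-age status is not reproducibly defined. Where late scans are used, the classification is open to error that runs mainly one way. The results exposed are the z-scores that depend on the 37-week standard and the extension comparisons by gestational age and size for gestational age. The rates named in section 9.12 and their planned precision are not.

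The size cannot be computed from the documents. The 12-19% is conditional on an infant being dated by a scan that under-dates by 1 week, and on the assumed gestational age distribution. The share of infants with such scans is not given. The directional comparison in step 4 further assumes that Dubowitz error is unbiased and that late scans have the same spread.

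**What to change.** Amend section 9.18.2 so that its statements on ultrasound, LMP and Dubowitz agree.

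1. Record the date and the source (record or recall) of each scan.
2. Give automatic first preference only to scans documented in records and done before a prespecified early-gestation cutoff.
3. State the rank of late or recalled scans, LMP and Dubowitz, and a rule for disagreement between them. Say where fundal height fits. Late scans should not simply fall through to LMP, since nothing in the documents shows LMP to be better.
4. Collect Dubowitz on all infants where feasible, with one per multiple set as now planned.
5. Record the dating method used for each infant.
6. Repeat the preterm/term and size-for-age results with Dubowitz-only dating as a sensitivity analysis.

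The cost is a few form fields and one extra analysis, largely on data the plan already intends to collect. Scan dates not captured at baseline may be hard to recover later. The downside is that some infants move to a noisier method, though one expected to be less biased in direction.

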9.18.3 Infant anthropometrics

Infant growth measures will include weight, length, head circumference, and mid-upper arm circumference (MUAC) according to the protocol in Appendix A. Trained members of the study team will be conducting the measurements per site.

9.18.4 Maternal anthropometrics

Maternal height, weight and mid-upper arm circumference will be captured at enrollment. Maternal weight and MUAC will be captured at 6 weeks postpartum, 6 month study visit and at the end of the 12-month study.

9.18.5 Infant feeding questionnaire

We will administer baseline and follow-up questionnaires on infant feeding/maternal lactation. An extended list of questions will be asked at 9 and 12 months and a shortlist may be asked during the check in phone calls. The infant feeding questionnaire will cover topics such as:

Description of feeds

- Feeds provided:
 - Breastmilk (Mother's own milk, Other mother's milk -), colostrum (at baseline), Donor Human Milk
 - Formula
 - Supplements
 - Other feeds (water, cow's milk, etc.)
 - Liquids
 - Semi solid / solid foods and specific food groups
- Method of feeding (direct breastfeeding, cup/palladai/spoon, bottle)
- Who advised/decided on the type of feed (clinic staff, mother, etc)
- Provider of feeds (mother, clinic staff, etc.)
- Timing of introduction of complementary feeds and reasons
- Frequency of feeds
- Self-efficacy of complementary feeding

Breastfeeding (this information will not be collected during the extension as it is not applicable anymore):

- Time to first latch or milk feed (global standard: within 1 hour of birth)
- Day (post-birth) achieved full milk production/established lactation (“coming to volume”)
- Exclusive breastfeeding duration
- Number of breastfeeding or expression sessions per 24 hours
- Expressed Breast Milk storage method (refrigerator, freezer, etc.)
- Breastfeeding adequacy measures, like frequency of feeds (average number of expressions/full breastfeeding episodes per day), duration of feeds, and direct observation if the infant breastfeeds during the interview (WHO IMCI criteria, LATCH score, PIBBS scale). In addition, we will use the NeoEAT-Breastfeeding Screener Tool to assess symptoms of problematic infant breastfeeding based on maternal self-report.
- Maternal Perceived milk insufficiency (PMI)
- Incidence of infection (e.g. mastitis) or troubles breastfeeding (e.g. engorgement)
- Reason for stopping/difficulty breastfeeding (e.g. mother decision; medically directed)
- Breastfeeding self-efficacy and social support
- Use of kangaroo mother care; separation of mother and infant
- IYCF support provided/program/education availability
- Influence of family/friends (social norms) on breastfeeding behavior

9.18.6 Infant health questionnaire

Information on infant health will be captured through a questionnaire to the mother or primary caregiver (i.e. self-report from mother/caregiver), and clinical records (when available). The infant health questionnaire will include the topics below. We will also pilot infant morbidity in-home diaries for mothers to record daily details on selected morbidities like diarrhea, vomiting and respiratory infections) that are most likely to influence infant feeding and growth. Diaries will be introduced at the Week 6 visit (when transitioning to monthly follow-up visits), and mothers will be instructed to fill the diaries to use as a recall aid for subsequent visits. An extended list of questions will be asked at 9 and 12 months and a short list may be asked during the phone calls.

Infant severe morbidities and need for clinical care

- *Diarrheal disease*
Including history of:
 - Persistent diarrhea (diarrhea that lasts for >14 days, often seen in infants who are malnourished)
 - Acute diarrhea (diarrhea lasting 14 days or less)
 - Severe diarrhea: diarrhea that is associated with signs of clinical dehydration including sunken eyes, lack of thirst, tenting with skin pinch, etc
 - Hospitalizations for diarrheal illnesses (Bhandari 2003)
- *Pneumonia/acute respiratory infection* - possible though maternal self-report and clinic records. Definition: cough or difficulty breathing plus either fast breathing or chest wall indrawing (WHO 2013).
- *Sepsis or other severe infection*

- Possible serious bacterial infection in a young infant: evidence of severe clinical illness in an infant aged 7-59 days per IMCI criteria
- Very severe febrile illness: Fever + danger signs in a child 60 days or older per IMCI criteria
- Positive blood culture or CSF culture at any age. This will be documented based upon maternal self-report, patient personal health records, or clinic record.
- *Malaria*, diagnosed by rapid test or parasitological confirmation will be documented based upon maternal self-report, patient personal health records, or clinic record.
- *Necrotizing Enterocolitis (NEC)*: Definitions (based on clinic records and maternal report):
 - (1) confirmed NEC – modified Bell’s stage II or greater with pneumatoisis or portal venous gas on abdominal x-ray as well as intestinal (abdominal distention, blood in stool, abdominal tenderness) and clinical features (temperature instability, apnea, bradycardia, lethargy, metabolic acidosis, thrombocytopenia). (Kliegman and Walsh 1987)
 - (2) suspected NEC – two of the following: abdominal distention, blood in stool, systemic features of lethargy/apnea/hypotonia. (Quigley 2018)
- *Seizures, neonatal encephalopathy* (based on clinical records)
- *Hyperbilirubinemia/Kernicterus* (based on clinical records)
- *HIV diagnosis*: A subset of children whose mothers’ test negative in prenatal testing may have subsequent exposure due to maternal peripartum HIV infection. We anticipate that these children will be at higher nutritional risk. Additionally, some percentage of children who are HIV exposed will seroconvert during the six-month follow up period. We will encourage testing of all children who do not grow adequately for HIV and will also encourage testing of all children with known HIV exposure at intervals per the country standard of care.
- *Hospitalization*: composite hospitalization for any reason. Clinic stay duration and discharge timing will be captured as well as supplementary feeds (e.g. nasogastric feedings, fortified feedings).
- *Malnutrition*: Severe acute malnutrition (SAM)/ moderate acute malnutrition (MAM)

Infant mortality (asked at all data collection time points, including follow up phone calls)

- Date and time of death
- Cause of death, if available via medical record, or verbal autopsy in Dar es Salaam.

